6. ELIGIBILITY CRITERIA

a) Inclusion Criteria - Inclusion criteria are the specific characteristics of the study population(s) required for study enrollment (e.g., ages, gender, condition or disease.) List the inclusion criteria in a bulleted list.

Response:

- 1. SD and SD/VT patients will have clinically documented ADSD or ABSD with and without positive effects of alcohol on their symptoms;
- 2. Age from 21 to 80 years.
- 3. Native English speakers.
- 4. Right-handedness (based on Edinburgh Handedness Inventory).
- b) Exclusion Criteria Provide specific criteria for determining ineligibility to participate. Provide justification for their exclusion (e.g., pregnant women).

Note: Exclusion criteria are not always clinical in nature. Exclusion may also include circumstances that interfere with:

- the participant's ability to give informed consent (diminished cognitive capacity or a language other than English and an interpreter unavailable)
- contraindications to the study treatment(s)/procedure(s)
- taking certain concomitant medication(s) or
- conditions that interfere with a patient's ability to comply with all study procedure(s)

Response:

- 1. Subjects who are incapable of giving an informed consent will be excluded from the study.
- 2. Pregnant and breastfeeding women until a time when they are no longer pregnant, or breastfeeding will be excluded from the study. All patients of childbearing potential will be required to agree to use a reliable method of contraception prior to and during the study. The method of contraception will be documented in the patient's research chart. All women of childbearing potential will undergo a urine pregnancy test, which must be negative for study participation.
- 3. All patients with a past or present history of the following conditions will be excluded from the study;
 - (a) Except for SD and dystonic VT, any neurological disorders, such as stroke, movement disorders, brain tumors, traumatic brain injury with loss of consciousness, ataxias, myopathies, myasthenia gravis, demyelinating diseases, drug dependence. Patients with tremor affecting other body parts will be excluded from the study. All patients who have dystonic movements in the body regions other than the larynx will be excluded from the study. This will allow maintaining the homogenous patient population and evaluating central drug effects without confounding by the presence of other neurological conditions.

- (b) Any psychiatric problems, such as schizophrenia, major and/or bipolar depression, obsessive-compulsive disorder, will be excluded to maintain the homogenous patient population and allow for the evaluation of central drug effect without confounding by the presence of psychiatric conditions.
- (c) Patients with a known past or present history of grade 2 or higher hepatic and renal dysfunction according to the NCI criteria will be excluded.
- (d) Patients with a known past or present history of moderate to severe congestive heart failure will be excluded.
- (e) Patients with a known past or present history of cognitive impairment and active suicidal ideations will be excluded.
- (f) Patient with a known past or present history of alcoholism and/or at high risk for alcohol use disorder according to the NIAAA definition (women > 7 drinks per week or 4+ drinks daily; men >14 drinks per week or 5+ drinks daily) and DSM-5 criteria (with ≥2 symptoms indicate alcohol use disorder) will be excluded.
- 4. Patients who are not symptomatic due to treatment with botulinum toxin injections into the laryngeal muscles will be excluded from the study until the time when they are fully symptomatic. The duration of positive effects of botulinum toxin vary from patient to patient, lasting on average 3-4 months. All patients will be evaluated to ensure that they are fully symptomatic prior to the entering the study.
- 5. To avoid the possibility of confounding effects of drugs acting upon the central nervous system, all patients will be questioned about *any* prescribed or over-the-counter medications as part of their initial intake screening. Those patients who receive medication(s) affecting the central nervous system (except for sodium oxybate) will be excluded from the study.
- 6. Patients will be asked whether they have undergone any head and neck surgeries, particularly any brain surgery and laryngeal surgeries, such as thyroplasty, laryngeal denervation, and selective laryngeal adductor denervation-reinnervation. Because both brain and laryngeal surgery may potentially lead to the brain structure and function re-organization, all subjects with a history of brain and/or laryngeal surgery will be excluded from the study.
- 7. Patients who have tattoos, ferromagnetic objects in their bodies (e.g., implanted stimulators, surgical clips, prosthesis, artificial heart valve, etc.) that are not MRI comparable and/or cannot be removed for the purpose of MRI study participation will be excluded from the study (for follow-up study).

NOTE: Per federal regulations, the risks and benefits of research must be fairly distributed among the populations that could benefit from the research. No groups of persons (e.g., gender, pregnant women, children, minorities, non-English speakers) should be categorically excluded from research without a valid scientific or ethical reason to exclude such groups.

c) Describe your rationale that the study population is representative of populations that may potentially benefit from the research, or the rationale for excluding certain groups, if applicable.

Response: N/A

7. RECRUITMENT PROCESS

NOTE: HIPAA does not permit non-MEE physicians to disclose patient information to Mass Eye and Ear for research recruitment. Non-MEE physicians may inform their patients of a research study and allow the patients to self-disclose their interest to the MEE study team.

Provide a detailed description of the recruitment plan (consistent with information you provide in the PRA), who is responsible for recruitment, how and when subjects will be recruited (i.e., flyers, advertisements, letters and oral/telephone scripts, email, at clinic appointments, etc.). Note: The HSC must review all recruitment materials. Please upload these materials into IRBNet with this submission.

Response: Patient volunteers will be recruited through MEEI Laryngology and MGH Neurology, advertisements in the Dystonia Medical Research Foundation and National Spasmodic Dysphonia Association newsletters and on their websites, advertisements in the local patient support groups, contacts with referring physicians as well as from the large pools of patients who have previously participated in our studies or have been seen for treatment by our research and clinical teams. Participants will be recruited regardless of their race, sex, age, religion, or national origin.

We will minimize the possibility of patients feeling obligated to participate when recruited by the investigators' own patients in the following ways.

We may ask a physician colleague to initially explain the study or may contact the patient in writing. We may explain the study at the first encounter, give the opportunity to take home the Consent Form, and re-contact the potential patient or ask them to call us back about their willingness to participate. We may recommend that the patient discuss participation with other health care providers.

During the first contact, the purposes, procedures, and risks of the protocol will be described in non-technical language and preliminary information about the present voice problems will be obtained. If the patient expresses an interest in study participation, an appointment will be scheduled for the informed consent, after which he/she will be interviewed to review background medical information, including voice, speech, language, swallowing, hearing, breathing, neurological, psychiatric diseases and disorders. In addition, the neurological, laryngological and cognitive assessments may be performed at this time.

The study procedures will be arranged as follows:

- Initial screening to establish eligibility,
- Covid-19 test for detection of infection prior to study participation, if applicable
- Review of medical information
- Informed Consent
- Questionnaires and rating scales
- Voice and speech recordings
- Blood or saliva sampled
- Alcohol/sodium oxybate/placebo administrations
- Data analysis and interpretation

8. CONSENT PROCESS

- a) 8a. Describe the consent process in detail. Include the following information:
 - who (e.g., physician, nurse, coordinator) will obtain consent,
 - their knowledge/experience in obtaining consent
 - location of the consent process
 - use of the Documentation of Consent Process Form
 - how the study information is presented (written consent form, orally, study information sheet, use of "short form" or translated consent etc.)
 - timing of consent (e.g., during pre-surgical visit, about one week before the screening visit)

Response: Consenting of patients will be done in a private room at MEEI Laryngology or MGH Neurology, with only research team members present. Subjects will be informed that they may choose not to answer a specific questions about their medical history, however, this may present one of the reasons for exclusion as determined by a research team. The PI or a licensed physician investigator, who have appropriate knowledge in obtaining consent, will obtain the consent. If consented by the PI, the consent of all subjects will be conducted at a time when a licensed MD on the research team is available either by phone or in person. Each subject will be offered the opportunity to have a conversation with a licensed physician, and the subject's decision will be formally documented. The General Research Consent and Authorization will be used to obtain written informed consent from all participants. All study procedures will be explained orally; all subjects will be given sufficient time to fully read the consent; all questions and concerns will be addressed before obtaining the subject's signature. Consent will be administered before any research procedures are performed.

b) 8b. How will you assess a subject's understanding of the research initially and over the course of the study? Is the presentation of study information appropriate for the study population (low vision, hearing impaired)? Describe specific provisions for subjects with limited understanding (e.g., a family member or other appropriate 3rd party is involved in the consent process).

Response: Subjects who are incapable of giving an informed consent will be excluded from the study. We will allocate sufficient amount of time on individual patient's basis to explain and answer all questions about the study procedures. We will ask questions to make sure the subjects understand the research study fully.

c) 8c. If the research-related intervention or interaction will occur on the same day that the subject initially receives information about the study, justify why this is appropriate/necessary.

Response: N/A

d) 8d. Describe provisions in place for non-English speaking subjects, including use of translators during the consent process and the translation of consent documents.

Response: Non-English speaking subjects will not be included into the study.

e) 8e. If a subject cannot read the consent form (e.g., low literacy, low or no vision) or cannot hear the person obtaining consent, explain how you will conduct the consent process and the provisions to accommodate subjects with limited or no hearing and/or limited or no vision.

Response: As impaired hearing, vision and speaking abilities most typically have neurological origins, these subjects will be excluded from the study.

9. STUDY PROCEDURES

a) Provide a detailed description of all study procedures and intervention(s) each subject and/or cohort will experience. Provide a schedule of visits and the procedures that occur at each visit (e.g., tests, questionnaires, surveys, imaging or other interventions.). If the study also involves standard of care, differentiate between research only procedures and standard of care.

Response:

Determine the clinical response of SD and SD/VT symptoms to sodium oxybate using a double-blind, placebo-controlled, randomized, cross-over study design.

The experimental design includes (1) screening for study eligibility; (2) an objective standardized alcohol challenge test for assessment of symptom responsiveness to alcohol, and (3) a double-blind, placebo-controlled, randomized, crossover study of sodium oxybate. The **primary outcome** will be to determine the response of SD and VT symptoms to sodium oxybate 40 min after administration, compared to placebo. We will recruit the following groups of patients:

- (1) ETOH+ SD and SD/VT who report positive effects of alcohol on their voice symptoms;
- (2) ETOH- SD and SD/VT who report no effects of alcohol on their voice symptoms, and Although our prior studies have shown that sodium oxybate has similar effects in both SD and SD/VT patients as well as in ADSD and ABSD, the inclusion of these patients will allow to capture the entire SD populations and to cross-validate our findings. On the other hand, the inclusion of negative controls with ETOH- SD and ETOH- SD/VT will allow for enhanced explanations of our findings and delineation of the primary factors contributing to the pathophysiology of SD and VT with respect to treatment outcome.

Enrollment and Eligibility Screening. Patient eligibility will be established based on the initial screening interview and the review of medical information, including laryngological and neurological examinations. Any subject with neurological (other than SD or dystonic VT in the patient groups), laryngeal, or a history of psychiatric problems will be excluded from the study. All patients will be right-handed, native English speakers according to the standardized Edinburgh Handedness Inventory (Oldfield, 1971), which will be important in examining drug-induced central effects during speech production. Because brain and laryngeal surgery may influence functional brain organization, all patients with a history of brain and/or laryngeal surgery will be excluded from the study. To avoid the possibility of confounding effects of drugs that act upon the central nervous system, patients who receive any medication(s) affecting the central nervous system will be excluded from the study. All patients will be asked to abstain from consuming any alcohol or caffeine (or foods with caffeine such as chocolate) for at least 48 hours before the study visits.

General Study Procedures. Eligible patients will require three visits, including one for the alcohol challenge test and two for sodium oxybate and placebo treatments (**Fig. 1**). At their initial baseline, all patients will be assessed for vital signs (blood pressure, pulse, height and weight); cognitive and

[figure not shown]

Fig. 1. Flowchart of study procedures. ETOH+ alcohol-responsive; ETOH- alcohol-non-responsive.

executive functions using the Montreal Cognitive Assessment (MoCA); prospective suicidality using the Columbia-Suicide Severity Rating Scale (C-SSRS), alcohol use disorder using NIAAA Recommended Alcohol Questions (Six Question Set) and DSM-5 Alcohol Use Disorder Questionnaire, daytime sleepiness using the Epworth Sleepiness Scale, voice/speech and dystonia symptoms (recordings and rating scales); blood will be sampled for genetic analysis. To reduce the burden to participants, some standardized assessments (Edinburgh handedness inventory) collected under the PI's other protocols within the last 12 months may be used in the same participants who agreed to the use of their data for other research studies. This will be done only in those participants who do not have any major changes in their health history at the time of intake screening for this study compared to the time when they participated in the PI's other protocols.

These evaluations will be repeated after alcohol/drug/placebo administrations, as described below. In addition, a questionnaire on side effects will be completed after administration of alcohol and treatments.

Voice and Speech Symptoms will be assessed using the patient's self-evaluation questionnaire and audio recordings of voice and speech samples. Patients will be

asked to produce various vocal tasks eliciting their symptoms, 20 sentences with high vowel content to elicit ADSD symptoms, 20 sentences with high content of voiceless consonants to elicit ABSD symptoms, and to tell a narrative story. Voice and speech samples will be audio recorded immediately before and after alcohol/sodium oxybate/placebo administrations based on a schedule defined below. Audio recordings will be de-identified, randomized and blindly rated to count the voice breaks as well as to quantify harshness, breathiness, tremor, and hoarseness using a visual analog scale with three gradation indicators along a 100-mm line (normal, modulates voice, offsets voice), with distance in mm denoting the degree of deviancy from normal, as described earlier (Kirke et al., 2016).

Alcohol Challenge Test. To determine the reliability and reproducibility of patients' self-reported benefits from alcohol on voice symptom, all patients will undergo the standardized alcohol challenge test for movement disorders (Knudsen et al., 2011; Haubenberger et al., 2013; Voller et al., 2014). Oral ethanol (40%, by volume) will be administered at a total dose of 0.8 g/L of the calculated total body water. It may be mixed into 50 ml of a sugarless, uncaffeinated drink, such as diet Sprite (Watson, 1989). The same dose of alcohol will be administered for the second time 30 min after the first administration. EPIC will be used for alcohol dispensing to ensure accurate and complete documentation. The alcoholic drink will be supplied by the MEEI Research Pharmacy. The test will be performed within fixed hours between 10am-12pm. The patients will be asked to drink their

predetermined amount of alcohol as fast as possible within 5-10 min. The levels of alcohol will be assessed using breath alcohol content (brAC) readings of the breathalyzer at eight time points, including twice before the alcohol challenge and at 15, 30, 45, 60, 120 min after alcohol intake (Haubenberger et al., 2013; Voller et al., 2014). Audio recording of voice and speech samples will be synchronized with brAC measurements and rated as described above.

Randomization and Allocation. Following the alcohol challenge, patients will be randomized for the double-blind, placebo-controlled, cross-over study. The randomization will be performed by the MEEI Research Pharmacy and will be blinded for the investigators and patients. The study will be conducted under the existing Investigational New Drug (IND) application granted to the PI by the US Food and Drug Administration (FDA) for the use of sodium oxybate in SD and SD/VT patients (#117,954). Patients will be allocated 1:1 to a treatment sequence #1 of sodium oxybate/placebo or sequence #2 of placebo/sodium oxybate. Jazz Pharmaceuticals, Inc., will provide sodium oxybate and the matching placebo for research purposes, which will be sent directly to the MEEI Research Pharmacy. The placebo will be a clear solution with salty taste that matches the appearance and taste of the drug. Sodium oxybate (1.5 g = 3 ml) of oral solution diluted in 47 ml of water) and the placebo (50 ml) will be formulated in sequentially numbered containers by the research pharmacy in the morning of administration. Both patients and investigators will be blinded until all outcome data are processed and the database is locked at the end of the study. EPIC will be used for study drug dispensing to ensure accurate and complete documentation.

Study drug will be administered by a licensed physician associated with this protocol.

As stated above under the *General Study Procedures* section, all patients will be assessed for their vital signs, MoCA, C-SSRS, side effects, and sleepiness immediately before and 45, 180, 300 min after drug/placebo intake. As a primary outcome measure, voice and speech recordings will be performed at the same time points. Data will be de-identified, randomized, and blindly rated for symptom severity, as described above. Our prior studies have shown that the effects of sodium oxybate (1-1.5 g) in ETOH+ movement disorders are obvious 30-45 min following drug intake and last approximately 3.5-4 hours (Frucht et al., 2005a; Frucht et al., 2005b; Arpesella et al., 2009; Simonyan and Frucht, 2013; Rumbach et al., 2016).

At discharge, patients will need to be stable and within 10% of their baseline assessment at the end of their fifth hour of monitoring. A licensed physician on the research team will evaluate and monitor patients who do not meet one or more criteria for discharge or have serious adverse events. If needed, the patient will be referred to the emergency department for a clinical care. No patient will be discharged without meeting the discharge criteria.

Patients will be required to confirm that they will not engage in important decision-making, financial and legal obligations for at least 12 hours after study participation. Patients with serious adverse events will be evaluated and referred to the emergency department for clinical care and/or admitted to hospital under [name] supervision.

Follow-up. We will follow up by phone, email or in-person with each patient after the study visits to assure that he/she has not developed any adverse side effects, in which case the patient may be asked to return to MEEI for additional evaluation. All patients will be given the contact information of the PI in order to report side effects/adverse reaction at any time.

b) 9b. Describe any data and/or sample banking, if applicable.

Response: Research data will be stored on the password-secured servers and password-secured image processing workstations located in the PI's laboratory. Hard copies of the results of the medical

history will be kept in the locked file cabinets located in the PI's laboratory. Only the research team will have access to the research data. Subject's identifying information will be removed and a unique research codes will be assigned for confidentiality purposes prior to data analysis. The list linking the code to the subject will be stored on the PI's password-secured server. All servers and workstations will be maintained by the Partners/MEEI IT. A database will be created, and this information/data will be encrypted using one of the software packages recommended in the MEEI IT and stored on a password-protected server with access limited to the PI and members of the research team.

c) 9c. If the study includes randomization describe the randomization process and randomization ratio, (include block size, permutations and stratification, if applicable.).

Response: Randomization will be performed by the MEEI Research Pharmacy as described in 9a.

d) If there are circumstances under which the researcher may withdraw participants, describe the conditions and process for withdrawal. Describe how subjects can withdraw from the study (e.g., calling or emailing the investigator/study coordinator).

Response: Subjects may stop taking part in this research study at any time without any penalty. This will not affect their ability to receive medical care at Partners/MEEI or to receive any benefits to which they are otherwise entitled.

Subjects may also withdraw their permission for the use and disclosure of any of their protected information for research, but they must do so in writing to the Principal Investigator.

Withdrawal without the subject's consent: The PI, the sponsor or the institution may stop subjects' involvement in this research study at any time without their consent. This may be because the research study is being stopped, the instructions of the study team have not been followed, the investigator believes it is in their best interest, or for any other reason. If specimens or data have been stored as part of the research study, they too can be destroyed without their consent.

The subject's participation in this study may be ended if he/she fails the screening procedure or if we detect brain abnormalities in her/his MRI, such as lesions after stroke and tumor. In that case, the subject will be informed and referred to a neurologist for further evaluation.

If subject screens positively as having active suicidal ideations based the Columbia-Suicide Severity Rating Scale (i.e., and answer of "Yes" to Question 4 or 5) or spontaneously expresses suicidality, the subject will undergo an emergent evaluation by a licensed clinical member of study staff for appropriate assessment and triage. As applicable, that triage may include escorting the subject to the Emergency Department for further evaluation.

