12. STATISTICAL METHODS

Describe the planned statistical methods including specific tests (e.g., parametric and non-parametric tests, estimation of incidence and prevalence rates, odds ratios, survival/failure analyses, intent to treat analyses). Provide the power calculations used to estimate the proposed sample size. If needed, please consult a biostatistician. (Note: Biostatistical consults are available through Harvard Catalyst.)

Response:

Audio recordings will be de-identified, randomized and blindly rated to count the voice breaks as well as to quantify harshness, breathiness, tremor, and hoarseness using a visual analog scale with three gradation indicators along a 100-mm line (normal, modulates voice, offsets voice), with distance in mm denoting the degree of deviancy from normal, as described earlier (Kirke et al., 2016). Alcohol Challenge Test. All individual measures before and after alcohol intake will be compared using the equation ((Baseline-Alcohol Challenge)/Baseline) \times 100%. To account for potential subjective bias and ensure reliable alcohol effects on voice symptoms, we will consider patients with \geq 10% change of their symptoms from baseline as responsive to alcohol (ETOH+) (Haubenberger et al., 2013; Voller et al., 2014). As a secondary outcome, we will compute Pearson's correlations between symptom scores and brAC measures to examine the baseline and each time point in respect to alcohol content at a corrected p \leq 0.05.

Analysis. The primary outcome within each group will be examined using a linear mixed effect model with treatment (sodium oxybate and placebo) and treatment visits as interacting fixed effects and a per subject random effect at overall $p \le 0.01$ to correct for multiple comparisons. If the interaction between the fixed effects is significant, the difference between treatments will be tested using linear contrasts of least-squares means for the fitted model at $p \le 0.05$ adjusted for multiple comparisons. As a secondary analysis, benefit ratio will be calculated as (sodium oxybate effect – placebo effect) and analyzed using a Friedman test at $p \le 0.01$.

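### The primary time point is inconsistent (40 min against recordings pre-dose and at 45, 180 and 300 min), and the primary model does not say which recordings enter it

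*Combined protocol and SAP*

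**What the plan says.** Section 9, in the description of the experimental design, fixes the primary outcome at one time: the response of symptoms to "sodium oxybate 40 min after administration, compared to placebo".

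Section 9, Randomization and Allocation, schedules the treatment-day assessments "immediately before and 45, 180, 300 min after drug/placebo intake" and then adds: "As a primary outcome measure, voice and speech recordings will be performed at the same time points". The same paragraph says that drug effects "are obvious 30-45 min following drug intake and last approximately 3.5-4 hours".

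Section 10 names clinical improvement of voice symptoms as the primary outcome and gives no time point.

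Section 12, Analysis, fits a mixed model separately in each patient group. Its terms are "treatment (sodium oxybate and placebo) and treatment visits as interacting fixed effects and a per subject random effect". Section 9, General Study Procedures, describes "three visits, including one for the alcohol challenge test and two for sodium oxybate and placebo treatments", so a treatment visit is one of the two crossover days. Section 12 does not say which recordings supply the primary outcome, how several recordings in one visit would be summarised, or whether the pre-dose recording is a baseline or an outcome value.

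**The concern.** Three statements have to fit together, and they do not. The named time has no scheduled recording. The recordings that do exist are tied to the primary measure at four times. The model that should produce the primary result cannot distinguish those times.

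At least three analyses of the same data are therefore open: 45 min alone, the three post-dose recordings, or all four. They estimate different quantities. Two of them would mix times when the protocol expects an effect with times when it does not. The trial is meant to test open-label findings under blinding and randomisation, so leaving this choice until the data are visible would weaken the main result whichever way it went.

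**Working it through.** **1. The times against the stated effect window.** Onset is 30–45 min and duration 3.5–4 h, that is 210–240 min. Counted from intake, the effect ends at 210–240 min. Counted from onset, it ends between 30 + 210 = 240 and 45 + 240 = 285 min. On either count 45 and 180 min lie inside the window, and pre-dose and 300 min lie outside it.

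**2. Does the sample size settle the time point?** Section 5a gives 22 patients for 80% power at 0.0125 by a binomial test, from 37/45 = 82.2% responders. The null rate and the sidedness are not stated. Assuming a null rate of 0.50 and a one-sided exact test, success needs at least 17 of 22, with exact alpha 0.0085 and power 81.6%; 22 is the first n to reach 80%. The figure reproduces. It concerns a responder proportion and involves no recording time, so it does not say which recording is primary.

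**3. Size of the estimate.** Assume the full effect at 45 and 180 min and none pre-dose or at 300 min. The average, as a share of the 45-min effect, is:

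- 45 min only: 1/1 = 100%
- three post-dose recordings: (1 + 1 + 0)/3 = 67%
- all four: (0 + 1 + 1 + 0)/4 = 50%

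If the effect at 180 min is only half, three recordings give (1 + 0.5 + 0)/3 = 50% and four give (0 + 1 + 0.5 + 0)/4 = 37.5%.

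**4. Power, as an illustration.** Assumptions not in the documents: a paired drug–placebo comparison with equal variance at each recording, and correlation rho between the drug–placebo differences at different recordings. From the plan: n = 22 (section 5a) and the 0.01 level (section 12), taken as two-sided. The standardised effect at 45 min is chosen to give 80% power under the noncentral t distribution with 21 degrees of freedom, which needs d = 0.79.

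Averaging m recordings multiplies d by f = (share of effect) / sqrt((1 + (m − 1)·rho)/m). For m = 4 and rho = 0.3, f = 0.5 / sqrt(1.9/4) = 0.5/0.689 = 0.73. For m = 3 and rho = 0.3, f = 0.667 / sqrt(1.6/3) = 0.667/0.730 = 0.91.

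| rho | 45 min only | three post-dose | all four |
|---|---|---|---|
| 0 | 80% | 91% | 80% |
| 0.3 | 80% | 71% | 46% |
| 0.5 | 80% | 59% | 34% |
| 0.7 | 80% | 49% | 26% |

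With 35 patients analysed, the recruitment ceiling per cohort, and the same d, three recordings give 93% at rho 0.3 and 77% at rho 0.7.

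**The case against.** The strongest defence is that section 12 models the primary outcome, and section 9 defines that outcome at one post-dose time. If 40 min is a nominal label for the 45-min recording, one value per visit enters, no time term is needed and nothing is averaged. The 5-minute gap is small, and 45 min is within the stated onset range. The sentence on recordings can also be read as naming the instrument and when it is used, without making each time a primary endpoint. All of this stands as a possible reading, but the documents do not choose it.

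The four-recording version is arguably the least natural. Improvement implies a pre-dose reference, and section 12 uses a baseline ratio for the alcohol test. That is fair, but section 12 states no baseline rule for the primary model.

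The second model factor might also have been meant as recording time, because the plan says "If the interaction between the fixed effects is significant, the difference between treatments will be tested using linear contrasts", which is easier to understand for time than for crossover day. The text says visits, however, and section 9 defines two treatment visits.

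The power figures rest on an assumed rho and a back-solved d. At rho 0 four recordings lose nothing and three gain. The figures also describe a direct treatment comparison, whereas section 12 contrasts treatments only after a significant interaction. They are illustrative only.

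**Conclusion.** The plan is wrong as written: the stated primary time has no recording, and the analysis does not identify which recordings it uses. That conclusion needs no assumption.

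A reader might go further and infer that the drug effect will be averaged with times of no effect, that the primary endpoint will go unmeasured, or that the trial is underpowered. The documents do not support these. Dilution occurs only if recordings other than 45 min enter the model. The 45-min recording is a close stand-in for 40 min. A power loss requires positive correlation between the drug–placebo differences, and its size depends on the number of patients analysed.

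If recordings are pooled, the estimate falls to one-half (four recordings) or two-thirds (three post-dose) of the 45-min effect. This holds for any rho, but assumes a full effect at 45 and 180 min and none at the other times.

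**What to change.** Before unblinding:

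- In sections 9 and 10, name the scheduled 45-min recording as the single primary time point, and reword the sentence on recordings so that the other times are not read as primary.
- In section 12, base the primary oxybate–placebo comparison on that recording, with the same-visit pre-dose recording as baseline and not as an outcome row. Either fit the model to the 45-min recording only, or take a 45-min contrast from a model with time and treatment × time terms. The second option should also allow for correlation between recordings from the same visit.
- Analyse 180 and 300 min as secondary.

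The cost is a wording amendment. It needs no new recordings, visits or patients, and the recording schedule stays as it is.
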